## 3 SELECTION AND WITHDRAWAL OF SUBJECTS

### 3.1 Inclusion Criteria

- i. Outpatient, male or female subjects of any race, 18 years of age or higher. Female subjects of childbearing potential must have a (-)UPT result at within 7 days of the first dose of study drug and practice a reliable method of contraception throughout the study;

*A female is considered of childbearing potential unless she is:*  
- *postmenopausal ≥ 5Y, without a uterus and/or both ovaries; or has been surgically sterile for ≥ 6M.*  
*Reliable methods of contraception are:*  
- *hormonal methods or IUD in use ≥ 90d prior to study drug administration, barrier methods plus spermicide in use ≥ 14d prior, or vasectomized partner.*

*[Exception: Female subjects of CBP who are not sexually active are not required to practice a reliable method of contraception and may be enrolled at the Investigator's discretion provided they are counseled to remain sexually inactive for the duration of the study and understand the risks involved in getting pregnant during the study.]*

- ii. Subjects with moderate plaque type psoriasis.
- iii. Physician Global Assessment (PGA) score of 3.
- iv. Able to understand study requirements and sign Informed Consent/HIPAA forms.
- v. Target lesion must be at least 2cm in diameter

### **3.2 Exclusion Criteria**

- i. Female subjects who are pregnant, breast-feeding, or who are of childbearing potential and not practicing a reliable method of birth control, or male subjects planning a pregnancy with their spouse or partner while in the study.
- ii. History of hypercalcemia or vitamin D toxicity or history of significant renal or hepatic disease
- iii. Patients with guttate, erythrodermic, or pustular psoriasis
- iv. Serious skin condition (other than psoriasis) or uncontrolled medical condition (in the opinion of the investigator).
- v. Skin conditions (e.g. eczema) that may interfere with evaluations of psoriasis.
- vi. Known hypersensitivity to Lexette or Sorilux Foam or any of its components.
- vii. Current drug or alcohol abuse (Investigator opinion).
- viii. Subject unable to commit to all the assessments required by the protocol.
- ix. Current enrollment in another clinical study and treatment with another experimental drug or approved therapy for experimental use within 30 days prior to the Screening Visit.

### **3.3 Withdrawal of Subjects**

It is the right and duty of the Investigator to discontinue the study participation of a subject when the subject's health or well-being is threatened by continuation in the study. Such subjects should be withdrawn from the study and not continued under a modified regimen. The following are circumstances that would result in the subject's discontinuation from the study:

- the subject experiences a serious adverse event rendering them unable to continue study participation;
- the subject is unable to physically or mentally tolerate the use of the test medication;
- an exclusion criterion becomes apparent at any time during the study; or
- the subject voluntarily withdraws.

In the event of premature discontinuation from the study, the Investigator should determine the primary reason for discontinuation.

If a subject withdraws for any reason, the subject will be replaced.

## 4 TREATMENT OF SUBJECTS AND FOLLOW-UP

### 4.1 Study Procedures

#### 4.1.1 Assessment Schedule

Procedures/Non-Procedure Description	Screening and Baseline	Weeks 2	Week 8
Informed Consent	X		
Medical History and Demographics	X		
Inclusion/Exclusion Criteria	X		
Initial Prior/Concurrent Medications	X		
Concurrent Medications subsequent visit		X	X
Vital Signs (includes height/weight)	X	X	X
Re-Randomization		X	
Abbreviated Physical Exam		X	X
VAS	X	X	X
DLQI	X	X	X
Complete Physical Examination	X		
TLSS scoring	X	X	X
Pregnancy Test	X	X	X
Adverse event assessment and reporting if applicable	X	X	X
Clinical severity/efficacy assessments by investigator (BSA, PGA)	X	X	X
Pharmacy Dispense and collection /Drug Accountability	X	X	X

#### 4.1.2 Screening Visit/ Baseline Visit

- Informed Consent/HIPAA
- Urine Pregnancy Test (*if applicable*)
- Subject Demographics/Medical History
- Concomitant Medication/Treatment
- Inclusion/Exclusion Criteria
- Assessments
  - BSA (*Affected Body Surface Area*)
  - PGA
  - TLSS

- Physical Exam
- Vital Signs with weight/height
- Subject assessment of pruritus VAS
- DLQI
- Drug dispensation
- Adverse events

#### 4.1.3 Week 2

- Urine Pregnancy Test (*if applicable*)
- Vital signs
- Concomitant Medication/Treatment
- Abbreviated Physical Exam
- Subject assessment of pruritus VAS
- DLQI
- Drug dispensation / collection
- Re-Randomization
- Adverse Events
- Collect & Weigh study drug
- Assessments
  - *BSA (Affected Body Surface Area)*
  - *PGA*
  - *TLSS*

#### Week 8

- Urine Pregnancy Test (*if applicable*)
- Vital signs
- Concomitant Medication/Treatment
- Abbreviated Physical Exam
- Subject assessment of pruritus VAS
- DLQI
- Drug collection
- Adverse Events
- Collect & Weigh study drug
- Assessments
  - *BSA (Affected Body Surface Area)*
  - *PGA*
  - *TLSS*

## 4.2 Study Treatment

### 4.2.1 Details of Study Treatment

#### Lexette Foam

Halobetasol Propionate Topical Foam is a hydroethanolic aerosol foam that contains a corticosteroid, halobetasol propionate. The chemical name of halobetasol propionate is 21 chloro-6 $\alpha$ , 9-difluoro-11 $\beta$ , 17-dihydroxy-16 $\beta$ -methylpregna-1, 4-diene-3,20-dione 17 propionate. Halobetasol propionate is a white to off-white crystalline powder with a molecular weight of 484.96 and a molecular formula of C25H31ClF2O5. It has the following structural formula: It is practically insoluble in water and freely soluble in dichloromethane and in acetone. Each gram of Halobetasol Propionate Topical Foam contains 0.5 mg of halobetasol propionate in a white to off-white foam base consisting of alcohol (specially denatured alcohol [SDA]), benzoic acid, cetostearyl alcohol, emulsifying wax, polyoxyl 20 cetostearyl ether, propylene glycol and purified water. Halobetasol Propionate Topical Foam is dispensed from an aluminum can pressurized with a hydrocarbon (isobutane and propane) propellant.

SORILUX Foam contains the compound calcipotriene, a synthetic vitamin D3 analog. Chemically, calcipotriene is (5Z,7E,22E,24S)-24-cyclopropyl-9,10-secochola-5,7,10(19), 22-tetraene-1 $\alpha$ ,3 $\beta$ ,24-triol. The structural formula is represented below: Molecular Formula: C27H40O3 Molecular Weight: 412.6 Calcipotriene is a white or off-white crystalline substance. SORILUX Foam contains calcipotriene 50 mcg/g in an aqueous-based emulsion foam vehicle consisting of cetyl alcohol, dibasic sodium phosphate, edetate disodium, isopropyl myristate, light mineral oil, polyoxyl 20 cetostearyl ether, propylene glycol, purified water, stearyl alcohol, dl- $\alpha$ -tocopherol, and white petrolatum. SORILUX Foam is dispensed from an aluminum can pressurized with a hydrocarbon (propane/n-butane/isobutane) propellant.

### Dispensation and Dosage Schedule

A 2-week supply of study medication will be dispensed at baseline and applied per instructions. A new supply will be given for 6 weeks per re-randomization.

Lexette foam will be applied twice daily and Sorilux foam will be applied twice daily 5 minutes after the Lexette application.

### 4.2.2 Treatment Assignment

All subjects who have signed an ICF will receive a 2-digit subject number, starting at 01. This subject number will be used to identify the subject throughout the study. When subjects qualify for the study, they will be randomized to study treatment groups utilizing treatment assignment numbers (TANs). Therefore, TANs are not the same as subject numbers. The next eligible subject will receive the lowest available TAN. The schedule will be prepared on a balanced 1:1 basis and will be available only to the member(s) of the site staff that is responsible for dispensing study treatment to the subject. Subjects withdrawn from the study will retain their subject number and their TAN, if

already allocated. New subjects will be allotted a new subject number and, if applicable, a new TAN.

## **Blinding**

Study treatments will be provided to subjects in a blinded-label manner . Investigator will be blinded.

### **4.2.4 Supplies and Accountability**

The Investigator or pharmacist will inventory and acknowledge receipt of all shipments of study medication. All study medication must be kept in a locked area with access restricted to designated study personnel. The study medication must be stored in accordance with the instructions provided with the shipment. The Investigator or pharmacist will also keep accurate records of the quantities of study medication dispensed and returned by each subject.

### **4.2.5 Treatment Compliance**

Subject compliance to study treatment regimen will be assessed at each visit; Patients will be instructed to bring study medication back at each study visit so that cans can be weighed and documented. Study personnel will ask each subject whether they missed any applications of study medication since the previous visit.

## **4.3 Concomitant Medication/Treatment**

Subjects must comply with the restrictions based on prohibited medications and treatments as detailed in the exclusion criteria. Other necessary therapies that will not interfere with the response to treatment may be provided at the discretion of the Investigator. The use of any concurrent medication, prescription or over-the-counter drug, is to be recorded in the source document along with the reason the medication was taken.

## **5 ASSESSMENTS OF EFFICACY**

### **5.1 Affected Body Surface Area Assessment (BSA)**

The area of body affected by psoriasis will be estimated as a percentage of the subjects total body surface area. As means to standardize measurements, the area of the subject's palm will be considered as 1% of total BSA.

### **5.2 Physician Global Assessment (PGA) – see attached table**

The Investigator will grade the current severity of psoriasis as per PGA

### **5.3 Target Lesion Severity Score (TLSS) see attached table**

The Investigator will grade the current severity of the target lesion per TLLS

## **6 ASSESSMENTS OF SAFETY**

### **6.1 Safety Assessments**

Throughout the study, subjects will be monitored for signs and symptoms of adverse events. All adverse events and con meds will be recorded throughout study. An *adverse event* is any pathological or unintended change in the structure, function or chemistry of the body that occurs during the study, irrespective of causality, including any illness, injury, toxicity, sensitivity, or sudden death. The condition must either not be present pre-study or must worsen in either intensity or frequency during the study. A *serious adverse event* is any untoward medical occurrence, that, at any dose:

- results in death;
- is life-threatening;
- requires in-patient hospitalization or prolongation of existing hospitalization;
- results in persistent or significant disability/incapacity;
- is a congenital anomaly/birth defect; or
- is an important medical event.

An *unexpected adverse event* is any treatment-related adverse event, which is not identified in nature, severity, or frequency in current literature on the test product.

### **6.2 Reporting Requirements**

#### **6.2.1 Serious and/or Unexpected Adverse Events**

Any serious or treatment-related unexpected adverse event occurring in this study must be reported to the IRB within the timelines stipulated by the IRB. In addition, SAEs will be reported to Leo Pharma within 1 (one) business day.

#### **6.2.2 Adverse Event Reporting**

All adverse events must be recorded by the Investigator into the CRF. The Investigator will be required to describe the adverse event, onset and stop date, severity, the course of action taken, if any, as well as any pertinent data necessary to allow a complete evaluation of the adverse event. For serious adverse events (SAE), an additional report (SAE report) must be completed.

#### **6.2.3 Follow-up and Final Reports**

Subjects who have had a serious adverse event must be followed clinically until all parameters, including laboratory values (if applicable), have either returned to normal or are otherwise explained.

If death was the outcome of the event on the initial SAE Report, a Follow-up/Final Report, including autopsy report, when performed, must be completed.

## **7 STATISTICS**

### **7.1 Sample Size Justification**

This is a descriptive study and a formal justification for the sample size is not necessary.

### **7.2 Analyses**

Statistical analyses will be conducted on an intent-to-treat population that includes all subjects who were enrolled and received study medication. Due to small sample size and exploratory nature of the study, descriptive statistics will be performed using SAS. Any additional statistical analyses will be performed as appropriate and detailed in the final report. All statistical tests will be two-sided and interpreted at a 5% significance level. Descriptive statistics (i.e., mean, standard deviation, etc.) will be provided for all continuous variables and frequencies for all categorical variables collected in this study. Summary tables will be used to present patient population characteristics at Baseline; data from the study questionnaires will be included. Analyses of study treatment will be performed using an ANCOVA technique with the Baseline value as the covariate provided the necessary assumptions for parametric tests are satisfied. The Wilcoxon Rank-Sum test will be used if the necessary assumptions for parametric tests are not satisfied. Mean scores will also be analyzed. Safety analyses will be performed in terms of incidence and severity of local tolerance signs and symptoms and adverse and/or unexpected events.

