### 1.1 Primary Endpoint

To observe the efficacy and safety of Lexette and Sorilux in moderate plaque type psoriasis for 2 weeks and then maintenance of success compared to vehicle with Sorilux for the next 6 weeks. Primary endpoint is the percent of subjects who maintain clear or almost clear on PGA at week 8.

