## 2 STUDY DESIGN

This is a single-center, double-blind study. Approximately 30 qualified subjects will be enrolled into a 8 weeks study. Subjects will be randomized to study treatment at a 1:1 ratio: of Lexette plus Sorilux for 2 weeks versus Lexette plus vehicle for 2 weeks. Those subjects who are clear or almost clear at the end of 2 weeks will be re-randomized into Sorilux for 6 weeks versus vehicle for 6 weeks at 1:1 ratio. All adverse events and con meds will be recorded throughout the study.

Group A n = 15	Lexette + Sorilux for 2 weeks
Group B n = 15	Lexette + plus Vehicle Foam for 2 weeks

Subjects will attend a Screening Visit/Baseline visit and if found eligible will be randomized to study treatment. Patients will be counselled on the use of the study medication and the medications will be labelled for the appropriate group as noted above.

Total study period is 8 weeks. Study visits will be, screening/baseline, week 2 and week 8. Study assessments will be at each visit: BSA, PGA, Itch VAS, DLQI, and TLSS in addition to standard medical assessments. There will be a standard prohibited medication/treatment and washout periods.

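### For PGA at week 2 the baseline-adjusted ANCOVA in section 7.2 reduces to an unadjusted comparison, because every eligible subject enters with PGA 3; Baseline TLSS could be named as the covariate instead

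*Combined protocol and SAP*

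**What the plan says.** Section 7.2 gives one general rule and names no endpoint: study treatment is analysed by an "ANCOVA technique with the Baseline value as the covariate", on condition that the parametric assumptions hold. If they do not, "The Wilcoxon Rank-Sum test will be used if the necessary assumptions for parametric tests are not satisfied". The same section provides "frequencies for all categorical variables collected in this study" and states that "All statistical tests will be two-sided and interpreted at a 5% significance level".

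Inclusion criterion iii in section 3.1 requires a "Physician Global Assessment (PGA) score of 3". Section 2 combines screening and baseline: "Study visits will be, screening/baseline, week 2 and week 8". The PGA that decides eligibility is therefore also the Baseline PGA.

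PGA at week 2 is listed among the secondary endpoints, with VAS, DLQI and TLSS. The schedule in section 4.1.1 collects TLSS and BSA at the screening/baseline visit as well as at weeks 2 and 8.

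**The concern.** The eligibility rule and the analysis rule do not fit together for this one endpoint. Own-baseline ANCOVA helps when the baseline score varies and predicts the outcome. Baseline PGA cannot vary among eligible subjects, so it cannot predict anything. Neither branch of the rule in 7.2 then adjusts week-2 PGA for baseline severity, and 7.2 does not say so.

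Two things are at stake, both modest. First, with about 15 subjects per group, precision that might be had from severity data already collected is left unused. Second, if the analyst notices the problem only at analysis, the choice between no covariate, TLSS and BSA would be made with outcome data in hand, since 7.2 leaves further analyses to be settled and described in the final report.

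**Working it through.** The plan states no power, effect size or standard deviation, so there is no planned figure to reproduce.

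**Inputs from the documents**
- Baseline PGA = 3 for every eligible subject (section 3.1, iii; one screening/baseline visit, section 2).
- 15 subjects in each of Groups A and B, 30 in total (section 2).
- ANCOVA with the baseline covariate, or the rank-sum test (section 7.2).

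**Step 1: what the ANCOVA does with a constant covariate.** The design matrix has three columns: intercept, group and Baseline PGA. The third column is 3 times the first, so the rank is 2 rather than 3. The slope on Baseline PGA cannot be estimated, but the group effect can.

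**Step 2: numerical confirmation.** One data set of 15 + 15 week-2 PGA scores was simulated. The score distributions were assumed and serve only to show the equivalence.

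| Analysis of week-2 PGA | Difference A - B | SE | Residual df | p |
|---|---|---|---|---|
| ANCOVA with the constant column | -0.867 | 0.322 | 28 | 0.0118 |
| Group only (two-sample t-test) | -0.867 | 0.322 | 28 | 0.0118 |
| Rank-sum test | n/a | n/a | n/a | 0.016 |

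The t-test on change from baseline also gives p = 0.0118. In 20,000 simulated trials under an assumed null distribution, the unadjusted t-test rejected 5.1% of the time, so test size is sound.

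**Step 3: one entry deviation.** If a single subject were enrolled with Baseline PGA 4, the covariate would no longer be constant. All it would do is remove that subject from the treatment contrast. In the simulated data the estimate with the covariate was -0.986 on 27 df, the same as after deleting the subject.

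**Step 4: what a covariate that varies would give.** Let r be the within-group correlation between Baseline TLSS and week-2 PGA. The documents give no value for r, so it is an assumption. The large-sample variance factor is 1 - r². With 28 within-group degrees of freedom, chance imbalance in a roughly normal covariate inflates the variance on average by 1 + 1/(28 - 2) = 27/26 = 1.038. The expected variance ratio, adjusted to unadjusted, is therefore (1 - r²) × 27/26.

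| r | 1 - r² | Variance ratio | Change in variance |
|---|---|---|---|
| 0 | 1.00 | 1.038 | about 4% higher |
| 0.3 | 0.91 | 0.945 | about 6% lower |
| 0.5 | 0.75 | 0.779 | about 22% lower |

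A simulation of 20,000 trials at 15 per group gave 1.04, 0.94 and 0.78, in agreement.

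Break-even: (1 - r²) × 27/26 = 1, so r² = 1/27 = 0.037 and r = 0.19.

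**The case against.** The strongest case against is that nothing is broken. The treatment effect can be estimated, and an unadjusted comparison of randomised groups is not an error. The rank-sum fallback needs no covariate and suits a 0 to 4 graded score. The study calls itself descriptive and exploratory. All of that stands, and it rules out several stronger readings that a reader might reach:

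- **That the ANCOVA fails for week-2 PGA.** It does not; steps 1 and 2 show it reduces to a valid comparison.
- **That the plan promises a baseline adjustment for PGA in particular.** Section 7.2 names no endpoint, and if PGA is treated as categorical its sentence on frequencies covers it.
- **That week-2 PGA is the principal induction outcome, or the only comparison using the full sample.** It is one secondary endpoint. VAS, DLQI and TLSS at week 2 compare the same randomised groups, and the own-baseline rule can work for them. The primary endpoint is at week 8.
- **That the result would be reported as adjusted when it is not.** No section says how it will be labelled.

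The size of the gain is also open to challenge. No document figure supports a correlation of 0.3 to 0.5. All subjects enter at one PGA grade, which the attached form defines by elevation, scaling and erythema, so TLSS may vary little at baseline. Below r of about 0.19, adjustment costs slightly more than it returns.

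What the objection does not remove is that 7.2 intends adjustment for baseline, cannot deliver it through Baseline PGA, and names no substitute although one is collected.

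**Conclusion.** The point holds as an inexpensive improvement, not as a flaw that endangers a result. It is certain that Baseline PGA is constant among eligible subjects and that own-baseline ANCOVA for week-2 PGA is then an unadjusted two-group comparison. There is no bias and no inflation of the type I error.

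The size of the benefit is conditional. It is about 6% to 22% lower variance if Baseline TLSS correlates 0.3 to 0.5 with week-2 PGA, nothing near 0.19, and about 4% higher variance at zero. It rests on the assumed correlation, on 15 subjects per group, and on TLSS varying among subjects who all have PGA 3. Sections 3.1 and 3.2 set no TLSS limits, so variation is possible, but its extent is unknown. The point does not bear on the week-8 primary endpoint.

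**What to change.** Add to section 7.2, in substance: Baseline PGA equals 3 by design and is not used as a covariate. PGA at week 2 (Group A versus Group B) is analysed by ANCOVA with Baseline TLSS as the single covariate. If the parametric assumptions are not met, the Wilcoxon rank-sum test is used as already planned. VAS, DLQI and TLSS keep their own Baseline values as covariates.

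TLSS is the more natural choice over BSA because section 5.3 makes it a severity grade, as PGA is, whereas BSA measures extent. It scores only one lesion, so its link to a global grade should not be taken for granted. The covariate should be fixed before unblinding and not chosen by its observed correlation.

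The cost is a few sentences, no new data and one degree of freedom (28 to 27). The risk is the roughly 4% rise in variance if Baseline TLSS proves unrelated to the outcome. If the sponsor prefers not to take that risk, the statement that week-2 PGA is compared without a baseline covariate is still worth adding. It makes the analysis explicit and avoids the entry-deviation effect in step 3.

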#### Secondary Endpoints:

PGA at week 2

VAS at week 2 and week 8

DLQI at week 2 and week 8

TLSS at week 2 and week 8

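### For itch VAS, DLQI and TLSS, the fallback test in section 7.2 drops the baseline adjustment, and the week-8 maintenance comparison is not told to adjust for the week-2 value

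*Combined protocol and SAP*

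**What the plan says.** Section 7.2 (Analyses) sets the main method: "Analyses of study treatment will be performed using an ANCOVA technique with the Baseline value as the covariate". It applies on one condition, "provided the necessary assumptions for parametric tests are satisfied". Otherwise, "The Wilcoxon Rank-Sum test will be used if the necessary assumptions for parametric tests are not satisfied". The section gives no diagnostic, threshold or timing for that judgement. It does not say whether the rank test uses the score itself or its change from baseline.

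The outcomes concerned are in the Secondary Endpoints list: "DLQI at week 2 and week 8", with VAS and TLSS at the same visits. The assessment schedule (section 4.1.1) collects all three at baseline, week 2 and week 8.

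On size and design, section 2 says "Approximately 30 qualified subjects will be enrolled into a 8 weeks study" and "Subjects will be randomized to study treatment at a 1:1 ratio", with 15 per group. Subjects who are clear or almost clear at week 2 are then re-randomised 1:1 to Sorilux or vehicle for six weeks. Their expected number is not given.

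On inference, 7.2 says "Due to small sample size and exploratory nature of the study, descriptive statistics will be performed using SAS", but also "All statistical tests will be two-sided and interpreted at a 5% significance level". Section 7.1 gives no sample size justification.

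**The concern.** Two things are lost or left open.

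First, the switch changes more than the distributional assumption. A two-sample rank-sum test on the score makes no use of the baseline value, so the comparison moves from adjusted to unadjusted as well as from means to ranks. Itch VAS, DLQI and TLSS are bounded scores that may well be skewed after treatment, so the fallback could be used often. With 15 per arm in induction, and fewer in maintenance unless every subject responds, baseline adjustment is precision that needs no extra subjects. A rank method that keeps the baseline exists.

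Second, the only covariate named is study Baseline. For the maintenance comparison the last value before randomised treatment is the week-2 value, recorded after two weeks of active therapy. It would normally predict week 8 better than a value taken before any treatment.

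Because the trigger is undefined, the choice between two analyses that can disagree would also be made with the outcome data in view.

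**Working it through.** The documents give no power, effect size, standard deviation or baseline correlation, so there is no planned figure to reproduce. What follows shows the size under stated assumptions.

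**From the documents:** 15 per arm at the first randomisation; two-sided 5% tests; ANCOVA on Baseline, otherwise Wilcoxon rank-sum.

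**Assumed:** a treatment shift of 1 SD on the log scale; baseline-outcome correlation ρ of 0 to 0.7; log-normal scores (log-scale SD 0.7); Shapiro-Wilk p < 0.05 on the ANCOVA residuals as the trigger; 7 per arm in maintenance.

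**Step 1: what adjustment is worth with normal scores.** Adjustment multiplies the residual variance by 1 − ρ². Power is approximately Φ(δ / (σ√(2/n)) − 1.96), with σ = √(1 − ρ²) after adjustment.
- Unadjusted, n = 15, δ = 1: 1/√(2/15) = 2.739; 2.739 − 1.96 = 0.779; power 78%.
- ρ = 0.5: σ = 0.866; 2.739/0.866 = 3.162; 3.162 − 1.96 = 1.202; power 89% (88.5%).
- The same formula gives 82% at ρ = 0.3 and 97% at ρ = 0.7.

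**Step 2: the plan's two-step rule on skewed scores, by simulation.** The first power column uses Wilcoxon as the fallback. The second changes only the fallback, to rank ANCOVA (ranked outcome on treatment and ranked baseline).

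| Per arm | ρ | Wilcoxon fallback | Rank ANCOVA fallback | Gain (points) |
|---|---|---|---|---|
| 15 | 0.3 | 72% | 76% | 4 |
| 15 | 0.5 | 76% | 82% | 6 |
| 15 | 0.7 | 79% | 92% | 13 |
| 7 | 0.3 | 37% | 38% | 1 |
| 7 | 0.5 | 41% | 44% | 3 |
| 7 | 0.7 | 51% | 55% | 4 |

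A repeat with 3,000 trials per cell gave gains of about 3, 7 and 13 points at 15 per arm and 1, 3 and 5 at 7 per arm. The simulation error of a single power figure is at most √(0.25/3000) = 0.9 points. At 15 per arm the trigger fired in 61-76% of trials.

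**Step 3: sensitivity to shape.**
- Heavier skew (log-scale SD 1.0), 15 per arm: 73% v 76%, 72% v 81% and 74% v 91% at ρ = 0.3, 0.5 and 0.7. At ρ = 0 it is 73% v 73%, so no gain.
- Heavier skew, 8 per arm: 40% v 43%, 42% v 48% and 50% v 60%.
- Normal scores, 15 per arm: the gain is 1 point or less (for example 93.9% v 94.9% at ρ = 0.7), because the trigger fires in only about 5% of trials.

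**Step 4: one rank ANCOVA throughout, with no switch.** In a run at 15 per arm (log-scale SD 0.7) this gave 76%, 83% and 92%, against 72%, 76% and 80% for the plan's rule.

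**Step 5: type I error.** With the mechanical trigger (normal or log-normal scores, log-scale SD 1.0 for the latter), the plan's rule gave 4.6-5.6% at 15 per arm and 4.8-5.4% at 8. Rank ANCOVA gave 4.0-6.0% across the cells run.

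**Step 6: covariate for week 8.** Assume correlations with the week-8 score of 0.3 for Baseline and 0.6 for week 2. Residual variance factors are 1 − 0.09 = 0.91 and 1 − 0.36 = 0.64, a ratio of 0.64/0.91 = 0.70. Simulated ANCOVA power at 7 per arm with normal scores was 41% v 53%. The direction is plausible; the size rests wholly on the two assumed correlations.

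**The case against.** **The Wilcoxon may be the better test on skewed data.** A reader might infer that the switch loses power exactly when scores are skewed. Against the ANCOVA it replaces, that is wrong at low correlation. With log-scale SD 0.7 and 15 per arm, Wilcoxon had 70% v 64% at ρ = 0 and 72% v 67% at ρ = 0.3; the two were about equal at 0.5, and ANCOVA led only at 0.7. This objection stands. The loss exists only against a rank method that keeps the baseline, and only if baseline predicts outcome.

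**The baseline may not be discarded.** Section 7.2 does not rule out a Wilcoxon test on change scores. In one simulated setting (log-scale SD 1.0, treatment raising the score) that gave 75% at ρ = 0.5 and 90% at 0.7, against 71% and 72% on raw scores. The rescue is not secure: in a separate run, the Wilcoxon on raw change scores did no better than on the scores themselves. The objection stands only so far as the text leaves the analysis variable open.

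**Baseline is a legitimate covariate at week 8.** It precedes re-randomisation, so adjusting for it introduces no bias. This stands; the issue there is efficiency.

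**The study is descriptive.** It has no power target, and the affected outcomes are secondary. The primary endpoint is a percentage, and every subject enters with a PGA of 3, so baseline PGA carries no information to lose. This stands and limits the weight of the point. It does not remove it, because 7.2 still commits to two-sided 5% tests.

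**Conclusion.** The point holds as a modest, inexpensive improvement to the secondary score analyses. As written, the fallback names no covariate although the baseline value is collected, and the covariate for the re-randomised comparison is not the value from which that comparison starts.

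Under the main assumptions, keeping the baseline is worth about 3-4, 6-7 and 13 points of power at 15 per arm for ρ = 0.3, 0.5 and 0.7, and about 1-5 points at 7 per arm. It is worth more under heavier skew, almost nothing if scores are near normal, and nothing if baseline does not predict outcome. The shift, correlations, distribution, trigger and maintenance numbers are all assumptions. The simulated scores are also unbounded and free of ties, unlike these scales. Restricting entry to PGA 3, and maintenance to clear or almost clear, may narrow the score ranges, which makes ρ = 0.7 the less secure end.

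A reader might also infer that choosing the test from the data inflates false positives. The simulations do not show that: type I error stays near 5%. They cover a mechanical trigger only, however. With a true effect and ρ from 0.3 to 0.7, ANCOVA and Wilcoxon disagreed on significance in 18-26% of trials at 15 per arm, so an undefined trigger leaves real discretion over which result is reported.

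**What to change.** In section 7.2, replace the conditional ANCOVA and Wilcoxon sentences with one prespecified baseline-adjusted approach that does not depend on a check of the outcome data. For example: *VAS, DLQI and TLSS will be compared by rank ANCOVA (ranked outcome on treatment and ranked pre-treatment value), with ANCOVA-adjusted mean differences reported alongside. The pre-treatment value is Baseline for the week-2 comparison and the week-2 value for the re-randomised week-8 comparison.*

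An acceptable alternative is ANCOVA as the main analysis with rank ANCOVA as a fixed sensitivity analysis, using the same definition of the pre-treatment value. It keeps the main result on the score scale, but on skewed data with low baseline correlation plain ANCOVA has less power than the present rule. Merely substituting rank ANCOVA as the fallback would repair the covariate and leave the data-driven switch in place.

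The cost is a few sentences, with no new data or visits and the same software. The downside is that a rank-based test gives no effect estimate on the score scale, so the adjusted mean difference must be reported with it. The change should be made before treatment codes are opened.
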